## 1.4 List of Abbreviations

Abbreviation	Definition
AE	adverse event
ALT	alanine aminotransaminase
ANCOVA	analysis of covariance
ANOVA	analysis of variance
AST	aspartate aminotransaminase
bid (b.i.d.)	bis en die, twice a day
BUN	blood urea nitrogen
cFGF23	c-terminal fibroblast growth factor 23
CFR	Code of Federal Regulations (United States)
CI	confidence interval
CKD	chronic kidney disease
CRO	contract research organization
ECG	electrocardiogram
eCRF	electronic case report form
EDC	electronic data capture
ESRD	end-stage renal disease
FAS	Full Analysis Set
FDA	(United States) Food and Drug Administration
FSH	follicle-stimulating hormone
GCP	Good Clinical Practice
GI	gastrointestinal
HD	hemodialysis
HDPE	high-density polyethylene
IB	Investigator's Brochure
IBD	irritable bowel disease
IBS	irritable bowel syndrome
IBS-C	irritable bowel syndrome with constipation
IBS-D	irritable bowel syndrome with diarrhea
ICF	informed consent form
ICH	International Committee on Harmonization
IEC	Independent Ethics Committee
iFGF23	intact fibroblast growth factor 23

Abbreviation	Definition
IRB	Institutional Review Board
IRT	Interactive Response Technology
ITT	intent-to-treat
IUD	intrauterine device
Kt/V	a measure of dialysis adequacy
LOCF	last-observation-carried-forward
MedDRA	Medical Dictionary for Drug Regulatory Activities
MMRM	mixed-effects for repeated measures
NHE3	sodium-hydrogen exchanger 3
PD	peritoneal dialysis
PP	Per-Protocol
PTH	parathyroid hormone
p-value	probability value
QRS	principal deflection in ECG
QT	ECG interval
QTc	QT interval which has been corrected by taking into account heart rate
RBC	red blood cell
RR	ECG interval between two consecutive R waves
SAE	serious adverse event
SAP	statistical analysis plan
SOP	standard operating procedure
s-P	serum phosphorus
TEAE	treatment-emergent adverse event
tid (or t.i.d.)	ter in die, three times a day
UN	unstructured
WBC	white blood cell count

## **2 INTRODUCTION AND BACKGROUND**

### **2.1 Introduction**

Chronic kidney disease (CKD) affects 5-10% of the population globally and the numbers of patients suffering from end-stage renal disease (ESRD) are increasing (Eknoyan 2005). With progressing impairment of renal function, the ability of the kidneys to appropriately excrete phosphate is reduced and hyperphosphatemia is a nearly universal complication of ESRD. Hyperphosphatemia is also part of the CKD Bone Mineral Disorder, which is associated with a disruption of normal serum and tissue concentrations of phosphorus and calcium, and changes in circulating levels of hormones such as parathyroid hormone (PTH) and vitamin D. Left untreated, hyperphosphatemia can lead to vascular and tissue calcifications, bone pain, fractures, and worsening secondary hyperparathyroidism and is associated with increased cardiovascular morbidity and mortality. Observational data show that treatment with phosphate binders to reduce hyperphosphatemia is independently associated with improved survival (Waheed 2013), and a meta-analysis of randomized clinical trials demonstrate that non-calcium-based binders have a lower mortality as compared to calcium-based binders (Jamal et al in the Lancet, published online 19 July 2013). Experimental studies provide support for the epidemiologic findings: phosphate excess promotes vascular calcification, induces endothelial dysfunction and may contribute to other emerging chronic kidney disease-specific mechanisms of cardiovascular toxicity (Waheed 2013). Hence, clinical treatment guidelines for patients with advanced kidney disease suggest maintaining serum phosphorus (s-P) within 3.5 to 5.5 mg/dL, which is close to the normal range (KDIGO Guideline 2009).

In addition to dietary phosphorus restrictions and dialysis, 80-90% of ESRD patients need treatment with oral phosphate binders. However, a large proportion of ESRD patients still do not achieve adequate phosphorus control (DOPPS Practice Monitor 2018). An important barrier for a successful treatment is the pill burden associated with all phosphate binders, which have to be dosed in several grams per day and taken with each meal to bind dietary phosphorus. The side effect profile with poor gastrointestinal (GI) tolerability and concerns for long-term negative effects such as tissue calcification, and potential metal accumulation toxicity from calcium-based and metal-based binders, respectively, further impair an effective phosphorus control in ESRD patients. There is, therefore, a rationale to develop oral phosphate-lowering medications with new mechanisms of action, a more convenient dosing, and improved risk-benefit profile.

Tenapanor is an oral, minimally absorbed compound that inhibits the sodium-hydrogen exchanger 3 (NHE3) transporter locally in the GI tract, which leads to reduced sodium and fluid absorption. Data from pre-clinical studies and results in healthy volunteers show that tenapanor also reduces the uptake of phosphorus from the gut.

Tenapanor reduces intestinal phosphate absorption, predominantly through reduction of passive paracellular phosphate influx, the most important overall mechanism of intestinal phosphate absorption. Tenapanor modulates tight junctions to increase the transepithelial electrical resistance, thereby reducing paracellular phosphate permeability; this effect is mediated exclusively via on-target NHE3 inhibition.

Tenapanor has been administered to approximately 347 healthy subjects at single doses up to 900 mg, and in repeated doses up to 180 mg/day for 7 days; to approximately 1020 subjects with irritable bowel syndrome with constipation (IBS-C), at doses up to 100 mg/day for up to 12 weeks; and to 477 CKD subjects (CKD Stages 3B, 4, and 5D) for up to 12 weeks at doses up to 120 mg/day.

## 2.2 Description of Investigational Product

Tenapanor is a GI-acting, minimally systemic, NHE3 inhibitor. Tenapanor is administered as the hydrochloride salt and is chemically described as: (S)-N,N'-(10,17-dioxo-3,6,21,24-tetraoxa-9,11,16,18-tetraazahexacosane-1,26-diyl)bis(3-((S)-6,8-dichloro-2-methyl-1,2,3,4-tetrahydroisoquinolin-4-yl) benzenesulfonamide) dihydrochloride. Its empirical formula is  $C_{50}H_{68}Cl_6N_8O_{10}S_2$ .

Tenapanor tablets will be supplied as yellow, oval biconvex film-coated tablets [REDACTED]

Dosing consists of one to three 10 mg tablets, taken twice daily just prior to breakfast and dinner (but not prior to the meal immediately prior to dialysis).

Tenapanor tablets (10 mg, administered as 10.6 mg of the hydrochloride salt) are packaged in an opaque white high-density polyethylene (HDPE) bottle (60/bottle) with a white polypropylene child resistant closure and induction seal plus a desiccant canister. Tablets of tenapanor should be stored in the original packaging according to the labeling.

### **2.3 Study Rationale**

Tenapanor is an investigational product being evaluated for its ability to lower s-P levels in CKD subjects on dialysis with hyperphosphatemia. Most ESRD subjects currently take phosphate binders to control s-P levels. A significant proportion of ESRD patients still do not achieve adequate phosphate control (DOPPS Practice Monitor 2018). Since tenapanor lowers s-P levels via a different mechanism of action, it is believed that adjuvant therapy of tenapanor with current phosphate binder therapy will produce additional phosphate-lowering activity. In rats, tenapanor dosed with sevelamer carbonate (a phosphate binder) significantly increased the amount of phosphorus in the feces as compared to administration of sevelamer carbonate alone; the increase in fecal phosphorus is an *in vivo* pharmacodynamic effect of phosphate lowering therapies.

### **2.4 Risk-Benefit Assessment**

The risk-benefit assessment of tenapanor is based on nonclinical toxicology, safety, and pharmacology studies as well as 19 clinical trials conducted with tenapanor. Results from the risk-benefit assessment are described in the Investigator's Brochure (IB).

Nonclinical toxicological studies of up to 9 months have been conducted in rodents and dogs. The toxicological profile includes soft stools and/or diarrhea and findings secondary to dehydration; these findings are an expected manifestation of the compound's exaggerated pharmacologic activity and findings were reversible during the recovery period without medication. A two-year carcinogenicity study in Sprague-Dawley rats was negative.

The safety, tolerability, pharmacodynamics and efficacy of tenapanor have been evaluated in 347 healthy subjects at single doses up to 900 mg, and in repeated doses up to 180 mg/day for 7 days; to 1020 IBS-C subjects at doses up to 100 mg/day for up to 12 weeks; and to 477 CKD subjects (CKD Stages 3B, 4, and 5D) for up to 12 weeks at doses up to 120 mg/day.

Tenapanor has minimal systemic bioavailability. Less than 1% of plasma pharmacokinetics samples collected during human studies (>3000 samples) have quantifiable tenapanor present in blood plasma (lower limit of quantification = 0.5 ng/mL); all samples with quantifiable tenapanor were below 1.5 ng/mL.

The reduction in sodium uptake results in an increase in net fluid volume in the intestinal tract. Based on this mechanism of action, tenapanor has the potential to produce softer or looser stools and increase stool frequency. Tenapanor has been demonstrated to be generally

safe and well tolerated in clinical studies. The safety profile with softening or loosening of stool consistency and GI adverse events (AEs) have been consistent with its pharmacology.

The theoretical AEs from tenapanor treatment in ESRD subjects would be due to exaggerated pharmacological effects and may include electrolyte disturbances, metabolic acidosis, soft stools/diarrhea, and reduced blood pressure. While a softening or loosening of the stool with an increased fluid loss via the intestine is an intended and desired effect of tenapanor in some subjects, sensitive subjects should be monitored for signs of dehydration in case of prolonged severe diarrhea. This study protocol includes clinical laboratory tests and vital signs. The health status of each study subject will be checked at each visit. All subjects will continue their existing treatment with phosphate binders when their participation in the study ends. See the IB for details on non-clinical and clinical results with tenapanor.

Subjects will be informed both verbally and in writing about these aspects before taking part in any study-specific examination. The study will be conducted under conditions that ensure a high probability for the early detection of untoward events and for appropriate intervention.

In summary, risks to participants in this short-term study are considered acceptable. Results from this study will be important for the development of a potential new drug, which could improve the treatment of hyperphosphatemia in ESRD subjects.

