### 1.3 Schedule of Assessments and Procedures

	Screening	Run-in Period		Treatment Period				
	Visit 1	Visit 2	Visit 3	Visit 4	Visit 5	Visit 6	Visit 7	Visit 8/ET
	Week -4 to -3	Week -2	Week -1	Day 1	Week 1	Week 2	Week 3	Week 4
Visit Window	-30 to -14 d	-18 to -7 (5-16 days after V1)	-9 to -2 (5-9 days after V2)	1 e (2-9 days after V3)	8 ± 2	15 ± 2	22 ± 2	29 ± 2
Study Procedure								
Informed Consent	X							
Inclusion/ Exclusion Criteria	X			X f				
Demographics	X							
Medical/Surgical History	X			X g				
Prior/Con Meds	X	X	X	X	X	X	X	X
Physical Examination	X							X
Weight (pre-dialysis)	X							X
Height	X							
Vital Signs a	X			X				X
12-lead ECG	X							X
Safety Laboratory Evaluations b	X							X
Serum Phosphorus	X	X *	X	X	X	X	X	X
FSH Test c	X							
Pregnancy Test c	X							X
Randomization				X				
Study Medication Dispense and/or Return				X	X	X	X	X
FGF23 and PTH Blood Sample				X				X
Biomarker Blood Sample				X				X
AE Assessment		X	X	X	X	X	X	X

\* At Visit 2, a serum phosphorus level of <5.5 mg/dL or >10.0 mg/dL does not deem the subject ineligible. However, the subject may be discontinued at the Investigator's discretion.

a Vital signs include sitting or supine blood pressure and pulse, prior to dialysis.

b Safety laboratory evaluations will include the hematology and serum chemistry tests other than the serum phosphorus test listed in Table 7-1.

c FSH (postmenopausal females) and pregnancy tests are performed on all females <60 years of age unless there is a documented method of sterilization, or FSH test confirms post-menopausal status.

d Screening (Visit 1) could be 14 to 30 days (i.e. 2 to 4 weeks) before randomization following the short-interval schedule.

e Day 1 is the randomization day and serves as the reference day for all visits.

f Subjects must continue to meet all applicable inclusion/exclusion criteria before randomization, including the criteria based on the s-P level at Visit 3.

g Record only changes to medical history from Visit 1

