**7.3.5 Analysis of Clinical Laboratory Tests**

A certified laboratory will be used to process and provide results for the clinical laboratory tests. The baseline laboratory test results for clinical assessment for a particular test will be defined as the last measurement prior to the initial dose of study medication.

For any laboratory test value outside the reference range that the Investigator considers clinically significant, the Investigator will:

- Repeat the test to verify the out-of-range value.
- Follow the out-of-range value to a satisfactory clinical resolution.

Record as an AE any laboratory test value that (1) is confirmed and the Investigator considers clinically significant, or (2) that requires a subject to be discontinued from the study, or (3) that requires a subject to receive non-study treatment, or (4) fulfills one or more criteria for serious adverse event (SAE).

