## **8 METHODOLOGY/STUDY VISITS**

### **8.1 Screening Procedures: Visit 1 (Days -30 to -14)**

The Investigator will inform each prospective subject of the nature of the study, explain the potential risks, and obtain written informed consent from the subject prior to performing any study-related procedures.

Screening evaluations will consist of the following:

- Assessment of the disease status outlined in the inclusion/exclusion criteria
- Kt/V – the most recent value prior to Screening
- Date of birth, gender, and race
- Weight (pre-dialysis) and height
- Medical and surgical history
- Phosphate binder currently used and prescribed daily dose (must be three times a day)
- Physical examination
- Vital signs (pre-dialysis)
- Electrocardiogram evaluation
- Blood sample for clinical laboratory chemistry and hematology tests (pre-dialysis)
- FSH and pregnancy test, if applicable
- Concomitant medications

Subjects will be instructed not to take any other medications without the approval of the Investigator (except their existing phosphate binder medication). Results of the screening evaluations must meet the inclusion/exclusion criteria for the subject to be enrolled in the study.

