#### **8.4 Visits 5, 6, and 7 (Days 8, 15, and 22 ± 2 Days)**

- Serum phosphorus measurement (pre-dialysis)
- Study medication dispensing and/or return, if applicable
- Concomitant medications
- AE assessment

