#### **8.5 Visit 8 (Day 29 ± 2 Days)**

- Weight (pre-dialysis)
- Vital signs (pre-dialysis)
- Blood collection for biomarker sample (pre-dialysis)
- Blood collection for FGF23 and PTH (pre-dialysis)
- Physical examination
- Electrocardiogram evaluation
- Blood sample for clinical laboratory chemistry and hematology tests (pre-dialysis)
- Blood sample for serum phosphorus (pre-dialysis)
- Pregnancy test (for women of child-bearing potential)
- Study medication return
- Concomitant medication
- AE assessment

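### Section 2.4 names electrolyte and acid-base risks and promises early detection, but no safety chemistry is scheduled between Screening and the end-of-treatment (or early termination) visit

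*Combined protocol and SAP*

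**What the plan says.** Section 2.4 says that the theoretical adverse events of tenapanor in this population "may include electrolyte disturbances, metabolic acidosis, soft stools/diarrhea, and reduced blood pressure". It then points to the monitoring in place: "This study protocol includes clinical laboratory tests and vital signs". It adds that each subject's health is checked at every visit, and concludes: "The study will be conducted under conditions that ensure a high probability for the early detection of untoward events and for appropriate intervention". It gives no frequency for the laboratory tests.

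The frequency is in Section 1.3, where the safety laboratory row is marked at Visit 1 and at Visit 8/ET and nowhere else. Footnote b defines that row and keeps it apart from the weekly phosphorus draw: "Safety laboratory evaluations will include the hematology and serum chemistry tests other than the serum phosphorus test listed in Table 7-1". Table 7-1 shows that the chemistry panel includes sodium, potassium, chloride and bicarbonate.

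The visit lists agree with the schedule. Section 8.1 has a chemistry and hematology sample at Screening (Days -30 to -14). Sections 8.2 to 8.4 have none at Visits 2 to 7. Section 8.5 has one at Visit 8 (Day 29 ± 2), the visit at which study medication is returned, and Section 8.6 repeats the Visit 8 evaluations at early termination.

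Section 7.3.5 takes the last value before the first dose as the laboratory baseline. It asks the investigator to repeat an out-of-range value judged clinically significant, and gives four routes by which a laboratory value becomes an adverse event. The first is: "Record as an AE any laboratory test value that (1) is confirmed and the Investigator considers clinically significant". The other three (discontinuation, non-study treatment, seriousness) do not mention confirmation.

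**The concern.** Electrolyte disturbance and metabolic acidosis are laboratory diagnoses that may give no symptoms. The protocol names both, cites laboratory tests and promises early detection with intervention, yet schedules no electrolyte or bicarbonate result until treatment is ending. Three things are at stake:

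- An asymptomatic change that arises and resolves between Day 1 and Visit 8 leaves no scheduled record, so the laboratory tables describe only the end of treatment.
- The change at Visit 8 is measured from a Screening value, because Visit 4 has no chemistry although blood is drawn then.
- A repeat sample taken to verify an abnormal Visit 8 value would normally be drawn after study medication has been handed back. Section 2.4 reports that the nonclinical findings reversed once dosing stopped. A normal repeat off drug would therefore not exclude a drug effect, yet it would leave the first route in Section 7.3.5 unmet.

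**Working it through.** **Inputs.** Visit 1 is 14 to 30 days before Day 1 (Section 1.3, footnote d). Visit 8 is Day 29 ± 2, so Day 27 to Day 31 (Sections 1.3 and 8.5). Treatment lasts 28 days (Section 3.1). Sample counts and volumes are from Table 8-1.

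**Step 1: reproduce the plan's own figures.** The visit lists give one chemistry sample at Screening and one at Visit 8/ET, 2 in all. Table 8-1 also has 2, at 7 mL each (14 mL). The table sums to 14 + 6 + 32 + 8 + 8 + 8 + 10 + 12 = 98 mL, as printed. The two-panel schedule is therefore consistent across Sections 1.3, 8 and Table 8-1. The only mismatch is with Section 2.4.

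**Step 2: scheduled blood work during treatment.**

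| Visit | Serum phosphorus | Electrolytes and bicarbonate |
|---|---|---|
| 4 (Day 1) | yes | no |
| 5 (Day 8) | yes | no |
| 6 (Day 15) | yes | no |
| 7 (Day 22) | yes | no |
| 8/ET (Day 29 for completers) | yes | yes |

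Scheduled chemistry at Visits 4 to 7: 0 of 4.

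**Step 3: time to the first post-dose result (completers).** Visit day minus 1: 27 - 1 = 26 days to 31 - 1 = 30 days after Day 1. That is essentially the whole 28-day treatment.

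**Step 4: age of the baseline and gap between panels.** From scheduled draws, the Section 7.3.5 baseline is the Screening value, 14 to 30 days before Day 1. The gap between the two panels for a completer is 14 + 26 = 40 days at the shortest and 30 + 30 = 60 days at the longest.

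**Step 5: blood volume if electrolytes were also reported at Visits 4 to 7.** The documents do not say whether the 4 mL phosphorus tube holds enough serum, so this is a range.

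- Existing tube suffices: 98 mL, unchanged.
- A 7 mL tube replaces the 4 mL tube at four visits: 98 + 4 × (7 - 4) = 110 mL.
- Replacement is the working assumption. If the laboratory instead wanted a separate 7 mL tube at each of the four visits, the total would be 98 + 4 × 7 = 126 mL.

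**The case against.** The strongest reply is that Section 2.4 is a general statement about untoward events. It commits to no laboratory frequency and rests on several safeguards: a health check at each visit, adverse event assessment at every visit from Visit 2, and watching for dehydration in prolonged severe diarrhea. It also refers to earlier exposure of 477 CKD subjects for up to 12 weeks, reported in an Investigator's Brochure that is not among the documents. Sparse chemistry may be justified there, and this cannot be judged from here. Safety is summarized descriptively without testing (Section 9.4.1), and randomization balances the age of the baseline, so an old baseline mainly adds noise rather than bias.

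Much of this stands, but it does not close the gap. The visit-by-visit safeguards work through symptoms or observation. Section 7.4.4 provides discretionary tests for following an adverse event already identified. Nothing in the schedule would prompt a test for a silent change.

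A reader might infer more than the documents support:

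- *That neither risk can be detected on treatment.* Visit 8 falls at or within days of the last dose and has a concurrent placebo group. A change still present then is visible and comparable. Subjects who stop early have the panel at the early termination visit.
- *That an abnormal final value would never be confirmed or recorded.* Confirmation is required only by the first of four routes in Section 7.3.5. That section does not exclude re-assay of the same sample, and it requires the value to be followed to resolution. Visit 8 values are summarized whether or not they are repeated (Section 9.4.9).
- *That the Day 15 end of dose adjustment makes matters worse.* Sections 4.1 and 6.1.3 tie adjustment to serum phosphorus and GI tolerability, not to electrolytes, and subjects can be withdrawn at any time.
- *That changes are most likely in the first weeks.* The documents give no timing.

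**Conclusion.** The point holds in a limited form. Section 2.4 and the schedule do not match: two laboratory risks are named and early detection is promised, but no safety chemistry is scheduled between Screening and Visit 8/ET. For a completer, the first post-dose result comes 26 to 30 days after Day 1, too late to support early detection during a 28-day treatment. What is lost is sight of asymptomatic changes in Weeks 1 to 3, a baseline close to the first dose, and normally the chance to confirm an abnormal end-of-treatment value on drug. What is kept is a randomized comparison of changes that persist to Visit 8/ET. An absence of laboratory signal would be informative about those, but not about transient changes.

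This rests on the scheduled draws alone. Unscheduled tests could narrow the gap for individual subjects, but not systematically. It also assumes that a repeat of a Visit 8 value means a new sample after study medication has been returned. The primary efficacy analysis and its power are unaffected.

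**What to change.** Reconcile Section 2.4 with Sections 1.3, 8.3 and 8.4, in one of two ways.

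1. Have the central laboratory also report the electrolytes and bicarbonate already in Table 7-1 on the pre-dialysis serum drawn at Visits 4 to 7. Update Sections 1.3, 8.3 and 8.4 and, if a larger tube is needed, Table 8-1. This gives a Day 1 baseline and weekly on-treatment values.
2. Keep the schedule and revise the early-detection statement so that it claims only what two panels, adverse event assessment and health checks can deliver.

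The first option costs assay fees and an amendment, with no new visit or venipuncture. Blood volume stays at 98 mL or rises to about 110 mL if the larger tube replaces the smaller one. Its downside is more out-of-range values for sites to review. The second costs only a text change, but leaves Weeks 1 to 3 unobserved. The clinical response to any value stays with the sponsor and the investigators.
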